Day	1	15	29	57	85	183	274	365	456	547	638	729		757	813	
Week	1	3	5	9	13	27	40	53	66	79	92	105		109	117	
Weeks elapsed since 1st dose	0	2	4	8	12	26	39	52	65	78	91	104		108	116	
Nominal months elapsed since 1st dose	0		1	2	3	6	9	12	15	18	21	24		25	27	
Procedures/ Assessments																

- b: Subjects who discontinue taking study drug prematurely for any reason will undergo an ED Visit within 7 days of their last dose of study drug. In addition, Follow-up Visits will be scheduled 4 and 12 weeks after the last dose of study drug (Visit 14 and Visit 15, respectively). Subjects who discontinue study drug before reaching 12 months of treatment will also be asked to return to the clinic for a 12 month clinical assessment and then again at 24 months. Subjects who discontinue treatment between 12 and 24 months of treatment will be asked to return to the clinic for a 24 month clinical assessment. Subjects who discontinue early from study drug are considered “on study” as long as they continue to return for their clinical assessments at 12 and 24 months as outlined above, at which efficacy (MMSE, CDR, ADAS- cog14) and quality of life (EQ-5D, QOL-AD and Zarit’s Burden Interview) will be assessed along with concomitant medications. New AEs will be collected for 4 weeks post last dose and followed-up for 12 weeks, or until resolution, whichever comes first. If >4 weeks post last dose only AEs relating to study procedures will be collected. These 12 and 24 month clinical assessment visits do not need to be attended if they fall within 8 days (visit window) after the ED Visit or within ±8 days of either of the Follow-up Visits (Visit 14 and Visit 15).

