9.7.1.1.4 EXPLORATORY ENDPOINTS

The exploratory endpoints of the study are:

- Time to change of concomitant AD treatment (ie, dose increase and/or initiation of treatment with AChEI or memantine after randomization) by 24 months
- The proportion of subjects at 24 months who received dose increases and/or initiation of treatment with AChEI or memantine after randomization
- The rate of change over time (mean slope) based on NPI-10 item score over 24 months
- Change from baseline in NPI-10 item at 24 months
- Change from baseline in EQ-5D (subject self-reported, study partner self-reported, and subject measured by proxy) and QOL-AD (subject and study partner) at 24 months
- Change from baseline in Zarit's Burden Interview at 24 months

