9.7.1.5 Prior and Concomitant Therapy

All investigator terms for medications recorded in the eCRF will be coded to an 11-digit code using the World Health Organization Drug Dictionary (WHO DD) (Mar 2014). The number (percentage) of subjects who took prior and concomitant medications will be summarized on the Safety Analysis Set by treatment group, Anatomical Therapeutic Chemical class, and WHO DD preferred term (PT). Prior medications will be defined as medications that stopped before the first dose of study drug. Concomitant medications will be defined as medications that (1) started before the first dose of study drug and were continuing at the time of the first dose of study drug, or (2) started on or after the date of the first dose of study drug up to the date of the last dose. All medications will be presented in subject data listings.

Medications taken within the 12-week Follow-up Period will also be recorded.

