9.7.1.6.1 PRIMARY EFFICACY ANALYSIS

The primary analysis will be based on an intent to treat philosophy without regard to adherence to treatment. The primary analysis of the change from baseline in CDR-SB at 24 months will be performed to compare elenbecestat 50 mg per day versus placebo using a linear mixed effects model for repeated measures (MMRM) on the FAS. The MMRM model will include fixed effects of treatment group, visit, treatment group by visit interaction, baseline CDR-SB, baseline CDR-SB by visit interaction, and randomization stratification variables (ie, region [7 levels], clinical dementia [yes, no], and concurrent AD medication use at randomization [Visit 2] [yes, no]). *ApoE4* status may be included in the model if appropriate. (revised per Amendment 05) An unstructured covariance matrix will be employed to model the covariance of within subject effect; if MMRM fails to converge then a covariance structure with fewer parameters from the following list will be employed according to the prespecified order in the list until the MMRM converges. The list of covariance structure will include Heterogeneous Toeplitz, Toeplitz, Heterogeneous Compound Symmetry, and Compound Symmetry. This primary analysis will include all observed post baseline data of the change from baseline in CDR-SB without imputation of missing values. The treatment effect for elenbecestat versus placebo will be compared at

24 months based on MMRM model. The LS means and difference in LS means between elenbecestat treatment group and placebo, and corresponding 95% CI will be presented.

The null hypothesis is that there is no difference in the mean change from baseline in CDR-SB at 24 months between elenbecestat 50 mg per day and placebo. The corresponding alternative hypothesis is that there is a difference in the mean change from baseline in CDR-SB at 24 months between elenbecestat 50 mg per day and placebo.

The primary analysis will be repeated to minimize the impact of change in concomitant AD medications where efficacy data after initiation of new AD medications and increase of current AD medications will be censored.

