Immune globulin IV, IVIG, IGIV	Carimune, Flebogamma, Gamimune N, Gammagard, Gamunex, Gammar-P IV, Iveegam, Octagam, Panglobulin, Vigam, Polygam S/D, Privigen, Sandoglobulin, Venoglobulin-S
Denosumab	Prolia (revised per Amendment 01)
Other monoclonal antibodies not listed here	

^aTopical, ocular, and inhaled formulations with minimal systemic exposure need not be prohibited. (revised per Amendment 03)

Listing 3 Prohibited Live/Live Attenuated Vaccines Within 3 Months Before Randomization and Until the Last Visit During the Treatment Period (this does not apply to non-live/inactivated vaccines)

Bacterial vaccines	Viral vaccines
Bacillus Calmette-Guérin vaccine against tuberculosis	Measles vaccination
Typhoid vaccination (oral)	Mumps vaccination
Cholera vaccination (oral)	Rubella vaccination
	Oral polio vaccination (Sabin)
	Yellow fever vaccination
	Varicella (chickenpox) vaccination
	Rotavirus vaccination
	Japanese encephalitis vaccination
	Live attenuated influenza vaccine (FluMist in the United States and Canada, and Fluenz in Europe)

This list is not exhaustive

Permitted Prior/Concomitant Medications

Listing 4 Medications Which Need To Be on a Stable Dose for 12 Weeks Before the Cognitive Assessments at Visit 2

Cognitive Enhancers	
Donepezil	Aricept
Rivastigmine	Exelon
Galantamine	Reminyl
Memantine	Namenda

Initiation, termination or change in dose is permitted if in line with local standard of care. Any changes are required to be stable for 4 weeks before any cognitive assessments.

Herbal medications or preparations should be discussed with the medical monitor. However, if they have claims of cognitive enhancements then they should follow the same rules as the medications in this listing. (revised per Amendment 05)

**Listing 5 Medications Permitted if Used on PRN or Short Term Basis (2 to 4 Weeks)
Which Are Not to be Used Within 72 Hours Before Cognitive Testing**

Generic name	Trade name
Benzodiazepines (revised per Amendments 03 and 05)	
Estazolam	ProSom
Alprazolam	Alprazolam Intensol, Niravam, Xanax
Triazolam	Halcion
Midazolam	Versed
Lorazepam	Ativan
Flunitrazepam	Rohypnol
Temazepam	Restoril
Clonazepam	Ceberclon, Klonopin
Diazepam	Diastat, Dizac, Valium
Chlordiazepoxide	H-Tran, Librium
Flurazepam	Dalmane
Sedatives	
Zopiclone	(various)
Zolpidem	Ambien; others
Ramelteon	Rozerem
Amitriptyline	(various)
Dothiepin	(various)
Risperidone	Risperdal
Olanzapine	Zyprexa
Promethazine	Phenergan; others

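### The supportive repeat of the primary analysis for AD-medication change censors only starts and dose increases, so CDR-SB data after permitted stops and decreases stay in

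*Protocol*

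**What the plan says.** Section 9.7.1.6.1 (Protocol, Amendment 05 text) states a purpose: "The primary analysis will be repeated to minimize the impact of change in concomitant AD medications". It then fixes the rule: "efficacy data after initiation of new AD medications and increase of current AD medications will be censored". Terminations and dose decreases are not named.

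Appendix 2, Listing 4, in the same version, covers donepezil, rivastigmine, galantamine and memantine and says: "Initiation, termination or change in dose is permitted if in line with local standard of care". The file also holds an older Listing 4 that asked for the same stable dose through Visit 15. Amendment 05 replaced it, and it plays no part here.

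Section 9.7.1.1.4 lists an exploratory endpoint, "Time to change of concomitant AD treatment (ie, dose increase and/or initiation of treatment with AChEI or memantine after randomization) by 24 months". Section 9.7.1.6.3 analyses that endpoint with the same pair of events.

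The primary analysis itself uses all observed post-baseline CDR-SB, whether or not the subject stayed on study drug.

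**The concern.** The stated aim concerns change in background AD treatment in general, but the rule reaches only half of the changes that the protocol allows. The omission is one-sided. Starting or raising a symptomatic drug would be expected to improve CDR-SB, and data after those events are removed. Stopping or lowering one would be expected to worsen CDR-SB, and data after those events are kept.

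If stops and decreases were equally common and had equal effect in both arms, little would follow. If they differ between arms, for example because background drugs are tolerated differently alongside study drug, the difference enters the estimate. More of them on elenbecestat would shrink an apparent benefit; more on placebo would enlarge it. The plan gives no basis for predicting which.

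This is the only named analysis in section 9.7.1.6.1 that deals with post-randomization AD-medication change. A reader would rely on it to judge whether the CDR-SB result owes anything to background therapy, and on that question it gives a partial answer.

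**Working it through.** **Matching permitted changes to the rule**

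| Post-randomization change in AChEI or memantine | Permitted by Listing 4 | Later CDR-SB censored under 9.7.1.6.1 |
|---|---|---|
| Initiation (including a switch to a different drug) | yes | yes |
| Dose increase | yes | yes |
| Dose decrease | yes | no |
| Termination | yes | no |

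The gap is the last two rows. It follows from the wording and needs no arithmetic.

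**The planned difference, for scale**

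Inputs from section 9.7.2: placebo mean change 1.46, reduction 25%, SD 2.05, dropout 30%, power 90%, two-sided alpha 0.05, 950 per arm.

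- Planned difference: 0.25 × 1.46 = 0.365.
- Evaluable per arm: 2 × (1.960 + 1.282)² × 2.05² / 0.365² = 663 after rounding up.
- Randomized per arm: 663 / (1 − 0.30) = 948, so 1896 in total against 1900 stated. The plan's figure reproduces.
- With 950 × 0.70 = 665 evaluable per arm, power is 90.1%.

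**Illustrative shift from leaving stops and decreases in**

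The documents give neither a rate nor an effect, so both are assumed. Shift = (difference between arms in the share with a stop or decrease) × (CDR-SB effect per event).

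| Arm difference | 0.25 point | 0.5 point | 1.0 point |
|---|---|---|---|
| 1 percentage point | 0.0025 (0.7%) | 0.005 (1.4%) | 0.01 (2.7%) |
| 3 percentage points | 0.0075 (2.1%) | 0.015 (4.1%) | 0.03 (8.2%) |
| 5 percentage points | 0.0125 (3.4%) | 0.025 (6.8%) | 0.05 (13.7%) |

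Percentages are of 0.365.

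**Illustrative cost of censoring them too**

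If a further share of month-24 values were removed (assumed), the two-sample calculation gives:

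- 2% removed: 651.7 per arm, power 89.5%
- 5% removed: 631.75 per arm, power 88.6%
- 10% removed: 598.5 per arm, power 86.9%

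These start from the full 665 per arm. The repeat already loses values to starts and increases, and the MMRM uses earlier visits, so they show the scale of the loss and are not the power of the repeat.

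**The case against.** The best defence is that the rule matches the protocol's own vocabulary. The exploratory endpoint and the exploratory objective on other AD pharmacotherapies both treat change as initiation or increase. An analysis aimed at new or intensified symptomatic treatment, which could mask decline, is a legitimate target. That stands as a reason to keep the present rule as one version. It does not close the gap: the endpoint measures escalation of need, whereas the repeat is meant to limit the influence of medication change on CDR-SB, and the protocol gives no reason for leaving out two permitted kinds of change.

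It is also fair that the stated aim is to minimize the impact, not to abolish it, and that background therapy is handled elsewhere. Concurrent AD medication at randomization is a stratification factor and a model term, further sensitivity analyses are foreseen, and cognitive testing waits for four weeks of stable dosing. The first concerns status at randomization, the second names no analysis of stops or decreases, and the third does not remove a lasting effect.

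Censoring after stops has a cost. Stopping may follow decline, so the missing values may be outcome-related and the analysis leans harder on missing at random. That stands, and is why both versions are wanted.

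Stronger readings are tempting but not supported:

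- *Changes after the last dose of study drug escape the rule.* A reader might infer this because section 9.7.1.5 counts a newly started medication as concomitant only if it "started on or after the date of the first dose of study drug up to the date of the last dose". That definition serves the tabulation of medications on the Safety Analysis Set. The censoring rule has no such cut-off, so on its wording a later start is censored. Table 5, footnote b, says of subjects already off study drug: "Subjects who discontinue treatment between 12 and 24 months of treatment will be asked to return to the clinic for a 24 month clinical assessment"; at these return visits efficacy and quality of life "will be assessed along with concomitant medications". The term is therefore not confined to time on study drug. Section 9.7.1.5 adds: "Medications taken within the 12-week Follow-up Period will also be recorded".
- *The time-to-change endpoint misses events in early stoppers.* Section 9.7.1.6.3 counts from randomization and censors subjects without a change by the end of study at their last concomitant-medication assessment. Nothing ties it to the last dose.
- *The 30% dropout allowance measures how many subjects are affected.* It only inflates evaluable to randomized numbers and says nothing about AD-medication changes.

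**Conclusion.** The point holds in a limited form. The repeat in section 9.7.1.6.1 is narrower than its stated aim: Listing 4 permits terminations and decreases, and CDR-SB after them is kept. An arm imbalance in those events would pass into the estimate.

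The size is unknown. The shift of 0.0025 to 0.05 point rests entirely on assumed imbalances and effects, and most of that range is small beside 0.365. The expected direction, that stopping or lowering symptomatic treatment worsens CDR-SB, is also an assumption that the documents do not quantify.

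The primary test, its alpha and the sample size are untouched. This is a worthwhile correction to a supportive analysis and does not threaten the main conclusion.

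**What to change.** In section 9.7.1.6.1, specify two versions of the repeat:

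1. CDR-SB censored after any post-randomization change in AChEI or memantine: initiation, increase, decrease or termination.
2. CDR-SB censored after initiation or increase only, as now.

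Report them side by side, with the number of subjects per arm having each kind of change, so that any imbalance in stops and decreases can be seen.

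The cost is wording: AD medications are already recorded during treatment, in follow-up and at the month-12 and month-24 return visits. The downside is somewhat more censored data in the new version and more reliance on missing at random, which the retained version helps a reader to judge. No change is needed to what Listing 4 permits.

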9.7.1.6.2 SECONDARY EFFICACY ANALYSES

Analyses for Key Secondary Efficacy Endpoints (revised per Amendment 05):

The key secondary analyses will be performed only if the primary analysis is significant. The treatment effect for elenbecestat 50 mg/day versus placebo, for each key secondary efficacy endpoint, will be tested using a sequential testing procedure at a significance level of 2-sided $\alpha = 0.05$, ie, any test will start only if the test with higher hierarchical order is significant.

The change from baseline in ADCOMS at 24 months will be analyzed using the same MMRM model as the primary efficacy analysis to compare elenbecestat 50 mg per day versus placebo on the FAS, using baseline ADCOMS in the model.

The change from baseline in amyloid PET SUVR at 24 months will be analyzed using the same MMRM model as the primary efficacy analysis to compare elenbecestat 50 mg per day versus placebo on the FAS, using baseline amyloid PET SUVR in the model. The same analysis will be performed within study as key secondary efficacy endpoint analyses.

Analyses for Other Secondary Endpoints (revised per Amendment 05)

The change from baseline in CDR-SB and ADCOMS at 24 months will be analyzed using the same MMRM model as the primary analysis for subjects enriched by baseline PET SUVR between e.g. 1.2 and 1.6 on the FAS.

The rate of change over time (mean slope) based on change from baseline in the CDR-SB will be analyzed using linear mixed effects (LME) models for multivariate normal data derived from a random coefficient model (slope analysis), where the mean slope in each group depends on a continuous assessment time. The LME model will include treatment group, baseline CDR-SB, randomization stratification variables, assessment time, baseline CDR-SB-by-assessment time, and treatment group-by-assessment time. ApoE4 status may be included in the model if appropriate.

Time to worsening of CDR scores by 24 months will be analyzed on the FAS using Cox regression model for treatment effect adjusting for randomization stratification factors. ApoE4 status may be included in the model if appropriate. (revised per Amendment 05) Time to worsening of a CDR score is defined as time from randomization to worsening of the CDR score (ie, the first worsening in 2 consecutive scheduled visits). For subjects whose CDR scores have not worsened by the end of the Treatment Period of the Core Study, the time to worsening of the CDR score will be censored at the date of last CDR assessment for these subjects.

Time to conversion to dementia for subjects who were not clinically staged as dementia at Baseline based on clinical diagnosis will be analyzed on the FAS using Cox regression model for treatment effect adjusting for randomization stratification factors. ApoE4 status may be included in the model if appropriate. (revised per Amendment 05) Proportion of subjects with dementia diagnosis at 24 months will be estimated using Kaplan—Meier method based on time to conversion to dementia based on clinical diagnosis. Time to conversion to dementia for subjects who were not clinically staged as dementia at Baseline based on clinical diagnosis is defined as time from randomization to conversion to dementia based on clinical diagnosis. For subjects without clinical dementia by the end of study, the time to conversion to dementia based on clinical diagnosis will be censored at the date of last dementia diagnosis.

The other continuous secondary efficacy endpoints as defined above will be analyzed using the same MMRM model as the primary efficacy analysis to compare elenbecestat 50 mg per day versus placebo on the FAS, using baseline value corresponding to the response variable in the model.

The relationship between clinical changes at 24 months (CDR-SB, ADCOMS, ADAS-cog14, MMSE, and FAQ) and changes in each of the biomarkers (amyloid PET, tau PET, CSF A β (1-x), t-tau, p-tau, vMRI, and fMRI) at 24 months, will be evaluated using an ANCOVA model. (revised per Amendments 03, 04, and 05) Changes in clinical scales at 24 months will be the response variables and either continuous or categorical change of biomarkers will be independent variables. The ANCOVA model will also include baseline value for clinical scale as a covariate, with treatment group and randomization stratification variables, as factors. ApoE4 status may be included in the model if appropriate. (revised per Amendment 05)

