- n: Amyloid PET scanning will be performed with a locally approved amyloid imaging agent (eg, Neuraceq, if available or an agent under clinical investigation if no agents are approved locally); for subjects participating in the amyloid PET substudy, the imaging agent must remain unchanged throughout the study. Subjects who are assessed by both amyloid PET and CSF are required to wait for a minimum of 48 hours between the 2 procedures (revised per Amendment 01). A positive amyloid result is needed for only 1 of the 2 amyloid eligibility procedures to confirm eligibility (ie, even if 1 of the 2 results is negative for amyloid, the subject would still be eligible under the other positive result). For subjects who are approved for rescreening, the amyloid PET need not be repeated for eligibility if confirmed amyloid positive during the original screening procedure. If a rescreened subject will participate in the longitudinal amyloid PET substudy, quantitative PET collection should be repeated if the original PET collection was done greater than 90 days from the date of the original screening procedure. (revised per Amendments 04 and 05)
- o: For those subjects who consent to the longitudinal CSF substudy, CSF should be collected at the same time of day for each assessment, preferably fasting or at least 2 hours post meal. For those subjects who consent to CSF and amyloid PET eligibility assessments, the 2 assessments should be separated by at least 48 hours between the 2 procedures. For these subjects, a positive amyloid result is needed for only 1 of the procedures to confirm eligibility (ie, even if 1 of the 2 results is negative for amyloid, the subject would still be eligible under the other, positive result). For subjects who are approved for rescreening, the CSF need not be repeated for eligibility if confirmed amyloid positive during the original screening procedure. A gravity drip collection method must be used. Subjects will be encouraged to stay at the site after completion of LP for medical observation. (revised per Amendments 04 and 05).
- p: Subjects receiving concomitant anticoagulation/antiplatelet therapy should have prothrombin time and INR (derived from prothrombin time) before LP; if they are assessed by the investigator to be at risk for bleeding, they are to be excluded from CSF collection. (revised per Amendment 01)

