- s: MRI scans are to include vMRI and fMRI sequences and will be read by an approved central reader. MRI imaging will be conducted on separate days from the scheduled visits. MRI imaging should be conducted within the 7 days before Visits 9 and 13. In the event of an Unscheduled Visit, the investigator in consultation with the medical monitor will determine whether or not a safety MRI should be conducted. If an ED Visit takes place, an MRI is to be conducted if not already performed during the preceding 90 days.
- t: Amyloid PET scanning (if subject has consented to optional substudy) will be performed with a locally approved amyloid β imaging agent (eg, Neuraceq, if available) or an agent under clinical investigation if no agents are approved locally; the imaging agent must remain unchanged for an individual subject throughout the study. An amyloid PET scan will only be performed at an ED Visit if the subject has been treated with study drug for at least 39 weeks and at least 6 months has elapsed since the prior amyloid PET scan was performed. (revised per Amendments 03 and 04)
- u: For subjects who consent to the tau PET longitudinal substudy, tau PET will be conducted at 24 months of treatment during the Core Study (or at the ED visit, provided the subject has received at least 39 weeks of study drug). At the 24 month timepoint (or at the ED visit), the amyloid and tau PET scans can be performed in either order but must be at least 48 hours apart. If the subject has also consented to the longitudinal CSF substudy, the longitudinal substudy assessments can be performed in any order, with at least 48 hours between each procedure. Tau PET scanning will be performed using a sponsor-supplied tau PET imaging agent, eg PI-2620. (revised per Amendment 04)
- v: Site staff will contact the subject or the study partner the day before the PK blood sampling to provide instructions that subjects must not take their study drug at home on the day of the PK blood sampling. During this telephone contact with the subject or the study partner, the site staff should document the time that the subject took their study drug that day, ie, the day before the PK blood sampling.

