9.7.1.1.2 SECONDARY ENDPOINTS

The key secondary endpoints of the study are as follows (revised per Amendment 05):

- Change from baseline in ADCOMS at 24 months in the combined studies
- Change from baseline in amyloid PET SUVR at 24 months for brain amyloid levels in the combined studies
- Change from baseline in amyloid PET SUVR at 24 months for brain amyloid levels in the individual studies

The other secondary endpoints of the study are as follows (revised per Amendment 05):

- Change from baseline in the CDR-SB at 24 months for subjects enriched by baseline PET SUVR, eg, between 1.2 and 1.6, in the combined studies
- Change from baseline in the ADCOMS at 24 months for subjects enriched by baseline PET SUVR, eg, between 1.2 and 1.6, in the combined studies
- The rate of change over time (mean slope) based on CDR-SB score over 24 months in the combined studies
- Time to worsening of CDR scores by 24 months (eg, the worsening of global CDR score is defined as an increase from baseline by at least 0.5 points on the global CDR scale on 2 consecutive scheduled visits at which global CDR is undertaken) in the combined studies

- Time to conversion to dementia by 24 months for subjects who were not clinically staged as dementia at Baseline based on clinical diagnosis in the combined studies
- Change from baseline in CDR-SB at 27 months (ie, 24 months of treatment plus 3 months posttreatment follow-up) in the combined studies
- Change from baseline in ADAS-cog14, MMSE, and FAQ at 24 months in the combined studies
- Change from baseline in ADAS-cog14 Word List (immediate recall and delayed recall) at 24 months in the combined studies

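### Amyloid PET agents may differ between subjects, yet the SUVR analysis has no tracer term or common scale, and one example SUVR window serves every agent

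*Protocol*

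**What the plan says.** All references are to the current (Amendment 05) text of the protocol.

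**Acquisition.** Table 4 (screening schedule), footnote n: "Amyloid PET scanning will be performed with a locally approved amyloid imaging agent". Neuraceq is given only as an example. Table 5 (Randomization Phase schedule), footnote t, gives the fallback for longitudinal scans, "or an agent under clinical investigation if no agents are approved locally", and requires that "the imaging agent must remain unchanged for an individual subject throughout the study". No agent is mandated across subjects, sites, regions or the two studies.

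**Analysis.** Section 9.7.1.1.2 has two key secondary endpoints in SUVR: "Change from baseline in amyloid PET SUVR at 24 months for brain amyloid levels in the combined studies" and "Change from baseline in amyloid PET SUVR at 24 months for brain amyloid levels in the individual studies". Section 9.7.1.6.2 puts them in the sequential procedure at two-sided 0.05 and specifies how they are analysed: "The change from baseline in amyloid PET SUVR at 24 months will be analyzed using the same MMRM model as the primary efficacy analysis", with baseline SUVR as the baseline covariate. Section 9.7.1.6.1 lists that model's terms: treatment, visit, treatment by visit, baseline, baseline by visit, region (7 levels), clinical dementia and concurrent AD medication, with ApoE4 as a possible addition. Tracer is not among them. Section 9.7.1 pools Studies 301 and 302.

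**Enriched analyses.** Two of the other secondary endpoints, change in CDR-SB and in ADCOMS, are restricted to "subjects enriched by baseline PET SUVR, eg, between 1.2 and 1.6, in the combined studies". The window is not tied to an agent.

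**The concern.** The primary model was written for CDR-SB, which is one instrument with one scale. It is carried over unchanged to a measurement whose unit may depend on the imaging agent. Holding the agent fixed within a subject protects that subject's change score. It does nothing to make scores comparable between subjects scanned with different agents.

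Two results are exposed. First, a pooled difference in SUVR would average effects expressed in different units, so its size and confidence interval would depend on how many subjects had each agent. The two individual-study effects could also differ merely because the studies' tracer mixes differ. Second, a baseline cut-off in SUVR would select different amyloid ranges for different agents. A model covariate cannot repair that, because it is a selection rule. Region in the model can absorb a mean shift where agent follows region, but not a ratio of scales and not a cut-off.

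**Working it through.** **The plan's own figure.** The only sample size derived is for CDR-SB (Section 9.7.2). With a difference of 0.25 × 1.46 = 0.365, SD 2.05, two-sided alpha 0.05 and 90% power, n per arm = 2 × 2.05² × (1.960 + 1.282)² / 0.365² ≈ 663. Dividing by 0.70 gives 948 per arm, 1896 in total, against 1900 stated. It reproduces and is not affected by this point. The protocol gives no SUVR mean, SD, effect or tracer mapping, so everything below rests on assumptions.

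**Assumed map between two agents.** SUVR_B = 1 + k(SUVR_A − 1), so SUVR_A = 1 + (SUVR_B − 1)/k.

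**Effect on the window.** Put 1.2 and 1.6 on B through the inverse, 1 + 0.2/k and 1 + 0.6/k:

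| k | 1.2-1.6 on B, expressed on A |
|---|---|
| 0.6 | 1.33-2.00 |
| 0.8 | 1.25-1.75 |
| 1.0 | 1.20-1.60 |
| 1.25 | 1.16-1.48 |
| 1.5 | 1.13-1.40 |

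At k = 0.6, subjects scanned with A enter at 1.20-1.60 and those scanned with B at the equivalent of 1.33-2.00. The two ranges share only 1.33-1.60.

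**Effect on the pooled difference.** If a share p of subjects has agent B and the true effect on A's scale is δ, the pooled SUVR effect is about δ × [(1 − p) + pk]. For δ = −0.030 and p = 0.5:

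- k = 0.6: −0.030 × 0.80 = −0.024 (20% smaller)
- k = 1.5: −0.030 × 1.25 = −0.0375 (25% larger)

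**Simulation check, on assumed inputs.** 300 subjects, seven regions, 2000 runs per setting. Baseline SUVR on A had mean 1.4 and SD 0.2; residual SD of change was 0.09; the effect was 0 (type I error) or −0.030. A one-visit ANCOVA with region and baseline stood in for the MMRM. Agent B was used either by half the subjects in every region or by everyone in three of the seven regions. Each cell shows these two layouts in that order.

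| k | Type I error, SUVR pooled | Mean estimate, SUVR pooled | Power, SUVR pooled | Power, common scale |
|---|---|---|---|---|
| 0.6 | 0.048, 0.050 | −0.0238, −0.0249 | 0.781, 0.790 | 0.808, 0.810 |
| 0.8 | 0.049, 0.057 | −0.0269, −0.0274 | 0.805, 0.805 | 0.810, 0.801 |
| 1.25 | 0.051, 0.050 | −0.0338, −0.0331 | 0.807, 0.803 | 0.809, 0.810 |
| 1.5 | 0.053, 0.050 | −0.0377, −0.0367 | 0.791, 0.801 | 0.805, 0.812 |

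Type I error stays near 0.05; the simulation standard error is √(0.05 × 0.95/2000) ≈ 0.005. The largest power loss is 0.8075 − 0.781, about 3 points. On the common scale the mean estimate is −0.030 throughout.

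**Would tracer covariates suffice?** Adding tracer and tracer-by-baseline terms to the SUVR model gave −0.0239 and −0.0249 at k = 0.6, and −0.0376 and −0.0367 at k = 1.5. These are essentially the unadjusted values. Such terms leave the treatment effect in mixed units.

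**The case against.** The best counter-argument is that SUVR derivation and harmonisation normally belong in the statistical analysis plan or a PET imaging manual. Neither is among the documents reviewed, and either could set a common scale. The protocol never says that SUVR is unharmonised. That limits certainty, but it does not dispose of the point: the protocol itself names the scale, the model with its terms, and an SUVR window, and those choices as written do not allow for agent.

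Some stronger readings are tempting and should not be drawn:

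- *The key secondary test is invalid or its alpha is inflated.* It is not. Agent is constant within subject, treatment is randomized, region is a stratification factor in the model, and the simulated type I error is preserved.
- *Different regions use different tracers.* The text permits this; it gives no list of agents by region and no mix. If one agent dominates, the effect is small.
- *The 1.2-1.6 window is fixed.* It is introduced as an example, and the enriched analyses lie outside the sequential procedure.
- *The within-subject rule concedes that agents are not interchangeable.* It is ordinary longitudinal practice. The documents say nothing about relative scales.

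**Conclusion.** The point stands as one of interpretation and subgroup definition, not of error control. If SUVR scales differ between agents, the pooled SUVR effect moves with tracer mix, by roughly −20% to +25% for k from 0.6 to 1.5 with agents split equally, and the example window mixes different amyloid ranges. The subgroup is the more serious of the two. The cost in power is small, at most about 3 points in the settings tried.

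The conclusion rests on three assumptions: that more than one agent is actually used, that their scales differ (here by an assumed linear ratio), and that no document outside those reviewed already sets a common scale. No stated figure in the protocol is wrong.

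**What to change.** Before unblinding:

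1. List the agents permitted and record the agent for each subject as an analysis variable.
2. For the key secondary MMRM, convert SUVR to a common standardised scale (eg, Centiloid). Alternatively, estimate the treatment effect within each tracer and combine the estimates on a standardised scale. Adding tracer, tracer-by-visit and tracer-by-baseline terms to a model still in SUVR units is not enough, and neither is averaging tracer-specific effects left in SUVR units.
3. Report SUVR results by tracer as supportive.
4. Define the enrichment window on the common scale, or separately for each tracer.

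The cost is a conversion by the central PET laboratory on scans already acquired and some added analysis work. It needs no new scans or subjects, and the 1900 total is unchanged.
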